5.3.7 Histopathology

For all participants who undergo at least one kidney biopsy during the first year post-transplant (either for cause or per institutional protocol), the kidney biopsy performed closest to the 12 month visit (but no later than 14 months post-transplant) will be submitted for central histopathology grading. During the central histopathology grading, published criteria will be used to diagnose the following: 1) antibody mediated changes, 2) acute cellular and ABMR, 3) borderline changes (suspicious acute TCMR), and 4) IFTA. The diagnosis of acute and chronic forms of ABMR will be based on C4d positivity with prior or current evidence of DSA during the study or evidence of chronic tissue injury, such as glomerular double contours, and/or peritubular capillary basement membrane multilayering and/or interstitial fibrosis/tubular atrophy and/or fibrous intimal thickening in arteries, also in-line with published criteria [Solez et al, 2008]. Biopsies will be regarded as suspicious for ABMR if C4d is not demonstrated in the biopsy, but morphologic evidence of tissue injury is nonetheless present, coincident with, or following DSA development [Solez et al, 2008].

Specimens will be similarly scored for g, t, v, i, cg, ct, ci, cv, ah, ptc, and mm in the manner previously described [Racusen et al, 1999]. Specimens will be regarded as positive for a particular feature if they receive a score > 0 for that particular characteristic. TG will be defined, for the purposes of this study, as cg > 0.

For specimens that are read locally, the above information will be extracted from the official biopsy report for inclusion in the eCRF.

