6. HLA-DQ DSA
7. DSA IgG₃ isotype
8. Requirement for antibody reduction therapy
9. eGFR at various thresholds (less than 30, 40, 50 mL/min/1.73 m² at one year or later; and a five-point decline)
10. Graft loss (defined as subject death, retransplantation, transplant nephrectomy, or a return to dialysis for at least a 6 week duration)
11. Mortality
12. BPAR (inclusive of ABMR and TCMR)
13. The four-part traditional composite endpoint: graft loss, local BPAR, mortality, and lost to follow-up (note – lost to follow-up will be summarized descriptively only)

GEE models used for analysis of treatment group differences will use the same covariates detailed in Section 7.4.1.1 with the exception of biopsy-based endpoints (i.e., TG and ABMR). In addition to the set of covariates from Section 7.4.1.1 biopsy-based endpoints will also include the covariates of CIT, WIT, KDPI, DCD status, and the three ex vivo perfusion parameters recorded pre-transplant. Similar to the primary endpoint, additional changes/details for the set of covariates will be included in the SAP.

For study purposes, lost to follow-up is defined as a subject failing to complete their final study visit no more than 30 days prior to the scheduled visit, and without a prior incidence of local BPAR, graft loss, or death. The incidence of lost to follow-up will be summarized with frequencies and percentage by treatment group.

The assessments of time to first occurrence for DSA, HLA-DQ DSA, C1q-binding DSA, DSA IgG₃ isotype, IA, TG, select BANFF histology grades (acute and chronic forms of ABMR, acute and chronic active TCMR, borderline changes, and IFTA), graft loss, mortality, local BPAR, and the four-part traditional composite endpoint will be summarized from the date of transplant. For patients who did not experience the endpoint event and/or were lost to follow-up or died prior to reporting the event, they will be censored at the date of their last known assessment/follow-up/death. Summaries will include estimable quartiles of time-to-first event with 95% confidence interval, Kaplan-Meier (KM) figures, and hazard ratios with 95% confidence interval. In the event that the median times are not estimable, the proportion of subjects with no DSA formation at the one and two year time points (as applicable) will be summarized by treatment group. Treatment group differences will be assessed with Cox regression models that account for the same covariates as used in the analogous GEE models.

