8 OPERATIONAL AND ADMINISTRATIVE CONSIDERATIONS

8.1 Procedure for Clinical Study Quality Control

8.1.1 Data Collection

The investigator or site designee will enter data collected using an Electronic Data Capture (EDC) system. In the interest of collecting data in the most efficient manner, the investigator or site designee should record data (including local laboratory values, as applicable) in the electronic case report form (eCRF) within 5 days after the subject visit.

The investigator or site designee is responsible to ensure that all data in the eCRFs and queries are accurate and complete and that all entries are verifiable with source documents. These documents should be appropriately maintained by the site.

The monitor should verify the data in the eCRFs with source documents according to the study monitoring plan.

Laboratory testing performed during the course of routine clinical care, including HLA typing and pre-transplant cross-match results, will be performed according to local standards. De-identified copies of HLA typing reports (donor and recipient) as well as recent pre-transplant local DSA testing results (if performed per SOC) will be sent to the central lab.

For the antibody and molecular assessments conducted by the central laboratory (performed at baseline, months 1, 3, 6, 9, 12, and 24), results will be compiled and the data electronically transferred to Astellas or its designee for inclusion in the clinical study database. The results of these central assessments for each participant will be shared with the corresponding Investigator. The results of the antibody assessments will be provided, as available (testing performed in batches), on an on-going basis, throughout the study. The results of the molecular assessments will not be shared with the corresponding Investigator until the end of the study.

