These threshold endpoints will be calculated for months 1, 3, 6, 9, and 12 using the Modification of Diet in Renal Disease (four variable-MDRD) criteria. Assessments are positive or negative.

- Five-point decline in eGFR

The decline in eGFR will be calculated with respect to the eGFR value at Day 30 visit.

- Traditional transplantation composite endpoint

Incidence will be assessed at month 12 for the following:

- Graft loss (defined as retransplantation, transplant nephrectomy, or a return to dialysis for at least a six week duration, or subject death)
- Death
- BPAR – positivity will be determined by local biopsy, central pathology, or reported adverse events.
- Composite occurrence of either graft loss, death, BPAR, and loss-to-follow-up

- Histopathology grading within 1 year

Central histopathology grading over 1 year will be diagnosed according to the BANFF diagnostic categories and subcategories that include the following:

- Normal
- Antibody mediated changes
 - C4d deposition without morphologic evidence of active rejection
 - Acute ABMR (grades: I, II, and III)
 - Chronic active ABMR
 - ABMR: either Acute ABMR or Chronic Active ABMR
- Borderline changes
- TCMR
 - Acute TCMR (grades: IA, IB, IIA, IIB, and III)
 - Chronic active TCMR
- IFTA (grades: I, II, and III)
- Other: all categorical findings will be summarized.
- In addition to the categories above, specimens will be given individual scores for the following: glomerulitis (g), tubulitis (t), intimal arteritis (v), mononuclear cell interstitial inflammation (i), early allograft Glomerulopathy (cg), tubular atrophy (ct), interstitial fibrosis (ci), vascular fibrous intimal thickening (cv), arteriolar hyaline thickening (ah), peritubular capillaries (ptc) and mesangial matrix (mm).

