7.4.2 Analysis of Secondary Endpoints

Risk factor analysis will be conducted in two parts. First, is to identify risk factors for outcomes based on factors measured at time of transplantation (baseline) including the pre-defined stratification factors. Last, is to identify risk factors for outcomes based on factors that are measured post-randomization and therefore, are subject to change e.g., average daily dose of MPA treatment or cumulative dose of corticosteroids. All models will include randomized treatment, irrespective of statistical significance. Models to assess risk factors for binary or categorical variables will be done using logistic regression. Odds ratio and 95% CI will be used as measures of strength of association and precision, respectively.

Risk factor analyses will be conducted for eight binary variables: IFTA, IFTA and Inflammation, BPAR, the four-part traditional composite endpoint, early MMF interruption/discontinuation, and eGFR status based on three thresholds 30, 40, and 50. The biopsy data are based on the central pathology results over the course of one year plus 2 months window. eGFR status variables are based on the assessment at Day 365 visit.

Each risk factor analysis model will include treatment group and a main factor: either De novo DSA, IA, or the composite of De novo DSA and IA. Following additional covariates will be considered for the two types of models, and a multicollinearity assessment will be proceeded for the final variable selection:

Risk factors measured at time of transplantation include:

- Cold ischemic time
- Warm ischemic time

- KDPI% \leq 50% (yes/no)
- KDPI% $>$ 50% (yes/no)
- HLA Class II mismatch (yes/no)
- Donor status (living/deceased)
- Donation after circulatory death (yes/no)
- Donor Age
- Donor-Recipient sex mismatch (match/mismatch)
- Donor-Recipient race mismatch (match/mismatch)
- Preservation by cold storage (yes/no)

Post randomization risk factors include:

- Cumulative Dose of Corticosteroids
- Average daily dose of MPA
- Mean dose level of tacrolimus
- Mean tacrolimus trough level
- Number of excursions below 80% or above 120% of the average tacrolimus trough level
- IPV estimated by CV%
- Post-transplant BK virus infection

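### The SAP 7.4.2 models of BPAR and the four-part composite on de novo DSA share a definition with their predictor, so part of any DSA odds ratio is built in

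*SAP*

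**What the plan says.** - **Predictor.** SAP 7.4.2: "Each risk factor analysis model will include treatment group and a main factor: either De novo DSA, IA, or the composite" of the two. The models are logistic, with odds ratio and 95% CI. SAP 7.1 sets two-sided 5% tests without multiplicity adjustment.
- **Outcomes.** SAP 7.4.2: "Risk factor analyses will be conducted for eight binary variables: IFTA, IFTA and Inflammation, BPAR, the four-part traditional composite endpoint", followed by early MMF interruption and three eGFR thresholds.
- **Content of BPAR.** Protocol 7.4.2 lists "BPAR (inclusive of ABMR and TCMR". The SAP does not take ABMR out.
- **ABMR rule.** Protocol 5.3.7, within the rules for central grading: "The diagnosis of acute and chronic forms of ABMR will be based on C4d positivity with prior or current evidence of DSA during the study". It continues with an alternative: "or evidence of chronic tissue injury, such as glomerular double contours" and other chronic lesions. A C4d-negative biopsy is called suspicious for ABMR only if the injury coincides with or follows DSA.
- **Source of BPAR.** SAP 6.1.2: "positivity will be determined by local biopsy, central pathology, or reported adverse events". SAP 7.4.2, directly after its list of outcomes, says the biopsy data come from central pathology.
- **Return of results.** Protocol 8.1.1: "The results of the antibody assessments will be provided, as available (testing performed in batches), on an on-going basis, throughout the study". Molecular results are held back until the end of the study.
- **Rate rule.** SAP 7.1 drops regression models for outcomes with an event rate below 10%, which it also expresses as fewer than 57 subjects.

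**The concern.** A risk-factor model asks whether patients with DSA go on to have more rejection. Here the outcome is partly assigned by looking at the predictor. A C4d-positive biopsy without chronic injury can be ABMR in a DSA-positive patient and not in a DSA-negative one. The null value of the odds ratio is then no longer 1, even if DSA carries no information about the tissue. Nothing orders the two in time: Protocol 5.3.7 accepts prior or current DSA, and SAP 7.10.3 counts central pathology to Day 426 and DSA to Day 386.

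What is at stake is interpretation. Protocol 1.1 argues for DSA as a surrogate for chronic immune injury and plans to correlate it with biopsy findings. A significant DSA–BPAR odds ratio would naturally be quoted in support. The same problem reaches the DSA/IA composite as predictor and the four-part composite as outcome.

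**Working it through.** **Figures in the plan.** The documents give no rate, effect size or power for this test. The total of 550 is reproduced: 220/(1−0.20) = 275 per group, and 2×275 = 550. The rate rule does not match it exactly: 57 is 10% of 570 and 10.4% of 550 (57/550).

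**Assumptions (none from the documents).** TCMR t = 10%; C4d lesion l = 5% or 10%; DSA prevalence d = 10% to 20%; all mutually independent, so DSA predicts nothing. The lesion counts as ABMR only if DSA is positive.

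**Rates and odds ratio.**
- DSA-negative: p0 = t = 0.100.
- DSA-positive: p1 = 1−(1−t)(1−l). For l=5%: 1−0.90×0.95 = 0.145. For l=10%: 1−0.90×0.90 = 0.190.
- OR = [p1/(1−p1)]/[p0/(1−p0)]: (0.145/0.855)/(0.1/0.9) = 1.53 and (0.190/0.810)/(0.1/0.9) = 2.11.
- Overall BPAR = d·p1+(1−d)·p0: from 0.1×0.145+0.9×0.1 = 10.5% to 0.2×0.190+0.8×0.1 = 11.8%.

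**Rejection rate of the two-sided 5% Wald test.** Simulated 2×2 tables, N=550, 0.5 added to each cell, no covariates. Details such as the 0.5 shift these figures by up to about three points.

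| Lesion | OR | DSA 10% | DSA 15% | DSA 20% |
|---|---|---|---|---|
| 5% | 1.53 | 22% | 27% | 30% |
| 10% | 2.11 | 54% | 65% | 72% |

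With TCMR alone as outcome the test rejects in about 4%.

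**Adding a 3% route to ABMR without DSA.** p0 = 1−0.90×0.97 = 0.127; p1 = 1−0.90×0.97×0.95 = 0.171 or 1−0.90×0.97×0.90 = 0.214. The OR falls to 1.41 and 1.87, and the test rejects in about 19% to 64%.

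**DSA/IA composite as predictor.** With IA assumed 10% and independent, the OR is diluted to 1.27–1.77 and the test rejects in about 13% to 55%.

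**Effect of the 57-subject rule** (no non-DSA route). At N=550 the expected events are 57.5 to 64.9. The binomial chance of at least 57, so that the model runs, is 55% to 87%. The model both runs and rejects in about 13% to 63% of trials; among trials where it runs, it rejects in about 23% to 73%. At N=440 (20% lost) the model runs in only about 5% to 25%. At N=300 and a 12% rate, 36 events are expected and the chance of 57 is about zero.

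**Denominator.** SAP 7.4 puts analyses of central pathology in the Biopsy Analysis Set but risk-factor analyses in the mFAS and PPS. Biopsies are not mandatory, so the biopsy set could be far smaller than 550.

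**The case against.** The best case against has five parts.

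1. *Central reading.* If the SAP 7.4.2 sentence on central pathology governs, local diagnoses and adverse event reports drop out, and the central reader is blinded to clinical results. This stands against the inference that investigators who know the DSA result label the outcome: the documents conflict on whether their diagnoses count. It does not remove the definitional link, because Protocol 5.3.7 is the central grading rule and cannot be applied in full without DSA. How a blinded reader obtains it is not stated.
2. *The IA model.* A reader might infer that the IA model has no built-in link, so DSA must look the stronger marker whatever the truth. The documents do not support that. Protocol 5.3.8 lets biopsies inform the molecular diagnosis when alternative pathology is recognized. The IA model is less affected, since no rejection category is defined by IA, but not free of any link.
3. *Rate rule and denominator.* The BPAR model may never run, and a small biopsy set makes that likelier. This stands, and it limits the practical reach. The rule selects whether the model runs; it does not correct the odds ratio.
4. *Invented rates.* This stands for the size. The direction follows from the definitions alone.
5. *Proportion.* Two of eight outcomes in an unadjusted secondary analysis of a trial described as exploratory are touched. IFTA, IFTA with inflammation and the eGFR thresholds are not defined by DSA. No formal hypothesis that DSA predicts rejection is written for these models.

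**Conclusion.** The point holds in a limited form. For BPAR and the four-part composite, part of any odds ratio for de novo DSA, or for the DSA/IA composite, is definitional and cannot be read as evidence that DSA predicts rejection. Under the assumed rates at N=550 the built-in odds ratio is 1.5–2.1 with about 22–72% rejection, or 1.4–1.9 with about 19–64% if 3% of patients reach ABMR without DSA. Allowing for the 57-subject rule, the model runs and rejects in about 13–63% (no non-DSA route).

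A reader might go further and conclude that the test must reject, or that the whole association is circular. Neither follows: TCMR and the chronic-injury route need no DSA, and a real association may sit on top of the built-in part. The randomized comparisons, primary and secondary, are unaffected.

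**What to change.** In SAP 7.4.2, for models whose main factor is de novo DSA or the DSA/IA composite:

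- Take as inferential rejection-related outcomes centrally scored findings defined without DSA: microcirculatory inflammation (g+ptc) and TCMR, subject to the SAP 7.1 rate rule. First reconcile the cut-off, which is at least 2 in SAP 6.1.2 and above 2 in SAP 7.4.2.
- Report the DSA odds ratios for full BPAR and for the four-part composite as descriptive, with a note on the shared definition.
- State whether the SAP 6.1.2 or the SAP 7.4.2 source of BPAR applies.
- Keep full BPAR for the treatment comparison and the IA-only model.

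The cost is wording and a re-derivation from Banff categories and scores already recorded; no new data are needed. The downside is fewer events. At TCMR 10% and N=550, 55 events are expected and the chance of reaching 57 is about 41%, so some models may end up descriptive. The change removes the definitional link only. A DSA result returned to a site can still prompt a biopsy and raise detection of any lesion.

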- To assess and compare, between treatment groups, the association/correlation of the appearance of DSA with each of the following: TG, chronic forms of ABMR, C1q-binding DSA, HLA-DQ DSA, DSA IgG₃ isotype, IA, histopathology, graft loss, various thresholds of eGFR ($< 30, 40, \text{ and } 50 \text{ mL/min/1.73 m}^2$), acute ABMR, TCMR, and mortality in patients who develop IA on molecular profiling in each cohort.
- To compare the MFI shift to a lower category (and magnitude of shift) between groups (including C1q MFI shift), in those patients who develop DSA during the course of the study.
- To examine percent MFI reduction within each subgroup over time in each treatment arm (including C1q MFI reduction) in those patients who develop DSA during the course of the study.
- To map expression results to known immunological pathways implicated in immune-mediated, kidney transplant tissue injury.

- To determine the longitudinal consequences of DSA formation and immune activation, perform de-identified, long-term follow-up through participating transplant centers in select study participants who provide the appropriate informed consent by future linking to the Scientific Registry of Transplant Recipients (SRTR) after completion of ASTOUND.
- To examine the economic burden of treating patients with molecular evidence of immune activation and DSA formation using Medicare claims data or commercial payer cost data in patients required to transfer from Medicare to private insurance.
- To compare outcomes in like patients between cohorts managed with maintenance protocol biopsy vs. biopsy for cause with respect to the composite endpoint, the components thereof, complications, and resource utilization.

Planned Total Number of Study Centers and Location(s):

Approximately 25-30 centers
US

Study Population:

Living or deceased donor kidney transplant recipients 16 to 70 years of age.

Number of Subjects to be Enrolled / Randomized:

550 patients to be enrolled.

Study Design Overview:

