While some transplant centers routinely perform protocol biopsies as part of their standard of care (SOC), others do not, despite the fact that there is compelling evidence that subclinical acute rejection present in the graft leads to chronic rejection and early graft loss. For this reason, a search for molecular biomarkers which can predict these phenomenon has been undertaken in the allograft, the urine, and the blood [El Ters et al, 2013; Li et al, 2013; Loupy et al, 2009; Kee et al, 2006; Moreso et al, 2006; Nankivell et al, 2004; Shishido et al, 2003; Nankivell et al, 2001; Kirk et al, 1999], the latter two of which having been proposed as a minimally invasive way to diagnose and monitor subclinical rejection, to optimize and personalize immunosuppression decisions, and as a means to potentially reduce the incidence of chronic rejection, which, in turn, could lead to significantly improved graft survival and function over the long-term. In fact, the need to complement histopathological grading with an interpretation of accompanying molecular signals was recently identified at the 2013 Banff Conference on Allograft Pathology [Haas et al, 2014]. However, up to now, relatively few individual molecular transcripts have been shown to correlate with chronic injury. Interestingly, an approach examining global genomic gene expression profiling in the peripheral blood was recently described. Using multiple, three-way classifier tools to validate 200 of the highest value probesets, the groups at Northwestern and Scripps have identified a variety of molecular signatures in the peripheral blood. Mapping these gene signatures to what is concomitantly revealed in biopsy specimens has demonstrated a sensitivity ranging from 82% to 100%, a specificity of 76% to 95%, a positive predictive value of 76% to 95%, and a negative predictive value of 79% to 100% [Kurian et al, 2014].

If similar methodology can be used to predict subclinical acute rejection, before the appearance of kidney dysfunction from the cumulative effects of tissue injury, this, too, could satisfy the necessary conditions for use as a surrogate marker.

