5.1.2 Increase or Reduction in Dose of the Study Drug(s)

After initial dosing, subsequent dosing in patients receiving either Astagraf XL or immediate-release tacrolimus should be predicated on clinical experience, patient tolerability, and monitoring of whole blood tacrolimus drug concentrations, the measurement of which, along with target tacrolimus levels, should be guided by individual center protocol and currently approved US Package Insert. For the ASTOUND study, the lower limit of acceptable tacrolimus trough concentrations in both the Astagraf XL and immediate-release tacrolimus treatment arms is 6 ng/mL for the duration of the study. If a prolonged period of reduced immunosuppression will be required to treat infection, sepsis, delayed wound healing, or other circumstances, patients should be removed from the study as per the discontinuation criteria (Section 6.1).

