7 STATISTICAL METHODOLOGY

7.1 General Considerations

All numeric and categorical efficacy and safety endpoints will be descriptively summarized. For continuous variables, descriptive statistics will include the number of subjects (n), mean,

standard deviation, median, minimum and maximum. Frequencies and percentages will be displayed for categorical data.

Summaries based on the FAS, mFAS, PPS, and BAS (e.g. disposition, baseline and efficacy data) will be presented by planned treatment group, unless specifically stated otherwise. Unless otherwise stated, all analyses will be performed using data pooled across sites. Subject listings of all data from the CRFs as well as any derived variables will be presented.

All statistical comparisons will be made using two sided tests at the $\alpha = 0.05$ significance level unless specifically stated otherwise. All null hypotheses will be of no treatment difference, all alternative hypotheses will be two-sided, unless specifically stated otherwise. P-values will not be adjusted for multiple comparisons. In the event that any analysis set sample size falls below 15 in any treatment group, descriptive statistics will exclusively be reported with no p-values or statistical inferences. In addition, logistic regression analysis and other regression model analysis as planned in the following sections will not be performed for outcome variables that have an event rate of less than 10% (i.e. reported by fewer than 57 subjects).

Unless otherwise specified, all data processing, summarization, and analyses will be performed using SAS[®] Version 9.4 or higher.

A hard database lock will occur prior to the final analysis.

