The primary analysis of the treatment group comparison will be based on fitting a multivariable binary logistic regression model with randomized treatment group (Astagraf XL group versus twice-daily, immediate-release tacrolimus group), pre-defined randomization stratification factors (planned use of Campath [Yes/No], levels of KDPI as defined in Section 4.5 of the protocol, and HLA Class II mismatch), recipient age, gender, and race, and pre-transplant cPRA included in the model. Investigational site will be included as a random effect. The limited numbers of subjects per center, however, may make it impracticable to include all sites in the statistical model. If reasonable, data from low enrolling sites (e.g., < 5 subjects) will be combined. The decision to include sites and how to combine sites, if necessary, will be made prior to database unblinding.

Adjusted (common) odds ratio (OR: Astagraf XL group versus immediate-release tacrolimus group) and two-sided exact 95% CI will be provided as measures of strength of association and precision, respectively. The null hypothesis of no treatment effect can be expressed as $H_0: OR = 1$ and will be tested at the ≤ 0.05 level using the Wald's chi-square statistic on one degree of freedom. Odds ratio will also be estimated for the covariates included in the model.

Subjects with primary endpoint unknown, undetermined, or missing will be excluded from the primary analysis.

The hypothesis for the comparison is as follows:

H₀: The proportion of subjects with the primary endpoint is the same between subjects receiving Astagraf XL and subjects receiving immediate-release tacrolimus.

H₁: The proportion of subjects with the primary endpoint is not the same between subjects receiving Astagraf XL and those receiving immediate-release tacrolimus.

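### The SAP 7.4.2 risk-factor models leave out site, so intervals for factors that vary between centres are too narrow, by an amount the documents do not fix

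*SAP*

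**What the plan says.** **Risk-factor models.** SAP 7.4.2 states: "Models to assess risk factors for binary or categorical variables will be done using logistic regression". Each model has forced terms: "Each risk factor analysis model will include treatment group and a main factor: either De novo DSA, IA, or the composite of De novo DSA" (combined with IA). Further covariates come from a baseline list and a post-randomisation list. The second includes cumulative steroid dose, mean tacrolimus dose and mean tacrolimus trough. Neither list contains site, and no random effect, GEE or clustered variance is mentioned. Separate models are planned for the twice-daily (BID) arm alone.

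**Site elsewhere.** The default in SAP 7.1 is "Unless otherwise stated, all analyses will be performed using data pooled across sites". The exception, in SAP 7.4.1.1, is the primary model: "Investigational site will be included as a random effect", with pooling of low-enrolling sites where reasonable. The later sentence in 7.4.2 that carries over the primary analysis covariates governs the treatment-group comparisons, not the risk-factor models.

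**Centre practice.**
- Tacrolimus: Protocol 5.1.2 says that monitoring, "along with target tacrolimus levels, should be guided by individual center protocol and currently approved US Package Insert".
- Steroids: Protocol 2.2.1 leaves peri-operative dose and duration to the centre's standard protocol. Protocol 5.1.3 and SAP 3.2 tie maintenance, taper and withdrawal to institutional protocol.
- Biopsy: Protocol 1.1 notes "While some transplant centers routinely perform protocol biopsies as part of their standard of care (SOC), others do not".
- The synopsis plans "Approximately 25-30 centers".

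**The concern.** Leaving site out does little harm when patients are randomised individually, because treatment is balanced within centres. Risk factors are not randomised. If patients at one centre share both a dosing habit and a tendency to have the outcome detected, they carry less independent information than their number suggests. An ordinary logistic model does not see this and reports intervals that are too narrow. The SAP thus models site where it matters least and omits it where it matters more.

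At stake is the first-listed secondary objective in SAP 3.1.2. A difference between centres in trough target, steroid policy or biopsy policy could appear as a significant association of trough or dose with BPAR or IFTA. SAP 7.1 adds "P-values will not be adjusted for multiple comparisons", so nothing downstream offsets the excess.

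**Working it through.** **1. Inputs.** The plan states no error rate for these models beyond the two-sided 0.05 of SAP 7.1. Patient numbers come from SAP section 4. Its sample size reproduces: 20% versus 10%, 80% power and two-sided 0.05 need 219 per group with continuity correction (plan: 220), and 220 / 0.8 = 275 per group. This gives 550 enrolled, 440 after dropout and 220 in the control arm after dropout. The number of centres is 25-30, and 27 is used below as a middle value. The outcome ICC and the share of a factor's variance that lies between centres are **assumptions**, because the documents give neither.

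**2. Formula.** With m patients per site (equal sites), the variance of the factor's coefficient is understated by

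DE = 1 + (m - 1) × ICC × share,

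and the actual type I error of a nominal 5% Wald test is 2[1 - Φ(1.96/√DE)].

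**3. Worked case.** 440 patients in 27 sites give m = 16.3. With ICC 0.05 and share 0.5, DE = 1 + 15.3 × 0.05 × 0.5 = 1.38. Then √1.38 = 1.18, so intervals should be about 18% wider. The actual error is 2[1 - Φ(1.67)] = 9.6%.

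**4. Formula results (actual error, nominal 5%).**

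| Patients, sites | ICC | share 0.3 | share 0.5 | share 1.0 |
|---|---|---|---|---|
| 440, 27 | 0.02 | 6.1% | 6.8% | 8.6% |
| 440, 27 | 0.05 | 7.7% | 9.6% | 14.0% |
| 440, 27 | 0.10 | 10.5% | 14.0% | 21.8% |
| 550, 30 to 25 | 0.02 | 6.2-6.5% | 7.0-7.5% | 9.1-10.0% |
| 550, 30 to 25 | 0.05 | 8.1-8.7% | 10.2-11.2% | 15.1-17.1% |
| 550, 30 to 25 | 0.10 | 11.2-12.5% | 15.1-17.1% | 23.6-26.6% |
| 220, 27 (control only) | 0.05 | 6.3% | 7.1% | 9.3% |

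At ICC 0.01, a purely centre-level factor with 550 patients gives 7.0-7.5%.

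**5. Simulation with unequal sites.** Two runs used 27 unequal sites and a factor with no true effect.
- 440 patients, 15% events, beta-binomial outcome, 1,000 trials: at ICC 0.05, 7.6%, 11.0% and 16.8% for shares 0.3, 0.5 and 1.0. At ICC 0.02 the range is 6.3-10.3%, and at ICC 0.10 it is 13.2-30.2%.
- 550 patients, 20% events, normal site effect on the logit scale, 800 trials: at ICC 0.05, 9.0%, 10.7% and 13.6%. At ICC 0.10, 10.0%, 12.8% and 21.1%.

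The second run defines ICC on the logit scale, which means less clustering of the observed proportions. That helps explain its lower figures for a purely centre-level factor. In an assumed biopsy subset of 250 with 30% events, it gives 7.3-10.4% at ICC 0.05 and 7.9-16.1% at ICC 0.10.

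**6. Negative controls (second run).** With outcome ICC 0 the error is 4.0-5.8%. With a factor that does not vary by centre it is 3.5-6.4%. The randomised treatment term stays at about 4-6%.

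**7. After accounting for site.** A random intercept brings the 550-patient figures at ICC 0.05 to 6.5%, 5.8% and 7.7%. Exchangeable GEE with a bias-reduced standard error and t on (sites - 1) degrees of freedom gives 4.7-6.7% across the 440-patient settings.

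**The case against.** The strongest reply is that size and premises are both softer than they look.

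- **Size is assumed.** This stands. At ICC 0.02, or when only 30% of a factor's variance lies between centres, the excess is often only one to four points.
- **Doses are individual too.** Protocol 5.1.2 bases dosing first on clinical experience, tolerability and monitoring, and sets a common trough floor of 6 ng/mL. Protocol 5.1.3 leaves steroid dose and duration to the attending physician. This stands as a limit: trough, tacrolimus dose and steroid dose are partly, not wholly, centre-driven. A share near 1.0 is an upper bound.
- **MPA dose and manufacturer.** A reader might infer that these cluster by centre as well. The documents do not show it: MPA dose is left to physician judgment, and outpatient product choice runs through retail pharmacies and vouchers (Protocol 2.2.1, 4.1.2).
- **DSA and IA.** The forced main factors are centrally assayed, and no error rate was computed for them.
- **Unbiopsied patients.** SAP 7.4 puts central-pathology efficacy analyses in the biopsy set, so they need not count as IFTA-negative. It also assigns risk-factor analysis to the mFAS and PPS, which leaves the set unclear. Even within the biopsy set, the mix of protocol and for-cause biopsies can differ by centre.
- **The trial is exploratory.** SAP 7.4.2 reports odds ratios and intervals without a rule for declaring a risk factor, and SAP 7.1 drops models for outcomes below a 10% event rate. This lowers the stakes and may leave fewer than eight outcomes. It does not make intervals offered as measures of precision correct.

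**Conclusion.** The point holds for factors that vary between centres. The omission is plain in the text, the centre-level drivers of trough, tacrolimus dose and steroid dose are documented, and so is variation in biopsy practice. The direction of the error follows: standard errors too small and intervals too narrow.

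The size is conditional on assumed ICCs and variance shares. Putting the formula and simulations together, the false-positive rate is roughly 6-10% at outcome ICC 0.02, 8-17% at 0.05 and 10-30% at 0.10. In the control-only models at ICC 0.05 it is about 6-9%.

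A reader might infer that risk factors will be declared well above 5% whatever the setting, or that the treatment comparison is compromised. The documents support neither. Without an ICC the first cannot be shown, and the randomised treatment term keeps its level. The eGFR thresholds are also a weaker case, since biopsy practice does not explain centre clustering in them.

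This is a cheap improvement worth making to a secondary analysis. It does not bear on the primary result.

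**What to change.** Add to SAP 7.4.2: *All risk-factor models, including those restricted to the BID arm, will account for investigational site, using the pooling of low-enrolling sites described in 7.4.1.1, by GEE with site as cluster or by site-clustered standard errors, with a small-sample correction.*

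The corrected clustered approach is preferred to a random intercept alone, which still leaves about 6-8% at ICC 0.05 with 27 sites.

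Splitting trough, tacrolimus dose and steroid dose into within-site and site-mean terms would help separate patient effects from centre policy. It should stay an optional sensitivity analysis, because the SAP revision history gives overfitting as the reason for trimming these models.

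The cost is a sentence of SAP text and one model option, with no new data. Intervals for centre-driven factors become somewhat wider, and GEE may occasionally fail to converge in the biopsy set, where clustered standard errors can be used instead.
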